7.3 Warnings and Precautions

7.3.1 Cytokine Release Syndrome

Cytokine release syndrome is a class effect of all T cell engagers and is due to an immune cascade following T cell activation. The tebentafusp regimen did not mandate prophylactic corticosteroids, antihistamines, or acetaminophen prior to dosing. Cytokine release syndrome was programmatically adjudicated using the ASTCT consensus grading for CRS (Lee, 2019). As of the DCO for this IB update, 344 (88.0%) of the 505 patients who received tebentafusp monotherapy across all clinical studies, experienced an AE of CRS that was considered related to study drug.

In IMCgp100-202 Study, which forms the largest dataset of programmatically derived CRS events, approximately 89% of patients following tebentafusp administration experienced CRS.

Most patients had Grade 1 (12%) or Grade 2 (76%) CRS. The incidence of Grade 3 CRS was 0.8%. There were no Grade 4 CRS or death due to CRS. The diagnosis of CRS following tebentafusp infusion was based most frequently on pyrexia followed by hypotension and infrequently hypoxia. Other commonly observed symptoms with CRS included chills, nausea, vomiting, fatigue, and headache.

Most patients experienced CRS following each of the first 3 tebentafusp infusions, with decreasing severity and frequency. In the majority of cases, CRS started on the day of infusion. Pyrexia was noted in nearly all cases of CRS, and in these patients, an increase in body temperature generally occurred within the first 8 to 10 hours after tebentafusp infusion. Cytokine release syndrome rarely (1.2%) led to treatment discontinuation. Cytokine release syndrome should be managed per the institutional protocol for CRS. In the absence of an institutional protocol, management guidance for hypotension and CRS with fluid management and IV corticosteroids has been included in all study protocols with tebentafusp. Based on the observed toxicities during the early weeks of dosing (eg,

hypotension), specific recommendations for close observation of subjects are included in each of the clinical study protocols.

7.3.2 Rash (Skin Toxicity)

Among the most frequent adverse reactions observed with tebentafusp are toxicity in the skin, most commonly rash, erythema, and pruritus. Typically, rashes were mild-to-moderate in severity and abated without systemic steroid intervention. Skin toxicity is likely related to its mechanism of action (induction of anti-gp100 T cell responses) given that melanocytes are known to express gp100, albeit at lower levels than in melanoma cells.

Across all studies, acute skin reactions occurred in 92.7% of patients treated with tebentafusp monotherapy, including any grade rash (grouped term, 85.3%), pruritus (71.5%), edema (grouped term, 28.7%), and erythema (25.1%). Most skin reactions were Grade 1 or 2 (72.3%) and some tebentafusp-treated patients experienced Grade 3 (20.4%) events. No Grade 4 or 5 events were observed.

Acute skin reactions typically occurred following each of the first 3 tebentafusp infusions, with decreasing severity and frequency. The median time to onset of acute skin reactions was 1 day in tebentafusp-treated patients and the median time to improvement to Grade \leq 1 was 6 days. There were no tebentafusp discontinuations due to acute skin reactions. The majority of symptoms resolved without any systemic corticosteroid or any long-term sequelae. No cases of Stevens-Johnson syndrome or toxic epidermal necrolysis were reported.

Management guidance for rash is included in all study protocols. In general, patients with symptoms associated with rash (eg, pruritus) can be managed with antihistamine and topical corticosteroid therapy. For more severe cases of rash, IV corticosteroid therapy has been implemented, generally in patients with multiple associated AEs (eg, rash associated with pyrexia, chills, and hypotension).

7.3.3 Elevated Liver Enzymes

Overall, an increase in any LFT occurred in tebentafusp as well as investigator's choice arms in IMCgp100-202 Study, but did not appear to be clinically relevant in either arm. Most of the ALT/AST elevations in the tebentafusp arm were mild, occurred early, and did not result in treatment discontinuation. No deaths due to ALT/AST elevations were observed and more than 90% of patients were able to continue tebentafusp treatment beyond worst grade ALT/AST elevation. A majority (70%) of ALT/AST elevations in the tebentafusp arm occurred within the first 3 infusions. Most tebentafusp treated patients who experienced Grade 3 or 4 ALT/AST elevations had improvement to Grade \leq 1 within 7 days.

Across all studies, approximately 35% of patients who received tebentafusp monotherapy have experienced LFT elevations/hepatotoxicity: 15.0% had Grade 1, 8.3% had Grade 2, 9.7% had Grade 3, and 1.8% had Grade 4 LFT elevations/hepatotoxicity. No Grade 5 events were observed. AST increased (17.6%), ALT increased (15.8%), hyperbilirubinemia (8.1%), and hepatic pain (5.5%) were the most common LFT elevations/hepatotoxicity events observed in monotherapy patients across all studies.

Treatment can include immunosuppression using corticosteroid therapy, although most cases have resolved without therapy. Patients experiencing this transient hepatotoxicity have been re-dosed with decreased severity after additional doses and subsequent return to baseline. Chronic elevations in LFT have been associated with disease progression. Management guidance for LFT elevation with conservative dose adjustments are included in all study protocols. With observation of elevations of transaminases during dosing with tebentafusp, corticosteroid therapy can be considered as described in the clinical study protocols.

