6. DOSING DELAYS/DOSE MODIFICATIONS

All dose modifications should be based on the worst preceding toxicity. See Appendix B for management of tebentafusp-related AEs.

For tebentafusp, escalation steps during interpatient dose escalation (ie, increasing from 20 mcg to 30 mcg or increasing from 30 mcg to 68 mcg) may be delayed. Dose reductions from 68 mcg are not permitted.

Weekly tebentafusp doses may be omitted as needed for management of AE. After completing 3 months of treatment, the Investigator may permit occasional, infrequent dose omissions to accommodate holidays, vacations, and the like.

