10.2 ON STUDY EVALUATIONS

All the assessments required as part of the study are indicated in the Study Calendar organized by visit date, with assessments required indicated with an “X” at the specific visits when they should be performed. Assessments required on C1D1 that are performed as part of the screening evaluations and within 72 hours prior to the first dose of study treatment do not need to be repeated on C1D1.

The following procedures will be performed during the treatment period:

C1D1

- Physical exam (short)
- Vital signs (Please see section 10.5)
- Relevant laboratory evaluations
 - Complete blood count with differential
 - Comprehensive metabolic panel (sodium, potassium, chloride, bicarbonate, BUN, creatinine, glucose, total protein, albumin, total bilirubin, total protein, AST, ALT, alkaline phosphatase, calcium), magnesium, and phosphorus
 - Amylase, lipase, CK, and LDH
 - PT (or INR) and aPTT
- Concomitant medications
- Administration of tebentafusp
- Recording of adverse events

CXD8, CXD15:

- Vital signs (Please see section 10.5)
- Concomitant medications
- Administration of tebentafusp
- Recording of adverse events

Cycle 2:

- Physical exam (short one, with weight)
- Vital signs (Please see section 10.5)
- Relevant laboratory evaluations
 - Complete blood count with differential
 - Comprehensive metabolic panel (sodium, potassium, chloride, bicarbonate, BUN, creatinine, glucose, total protein, albumin, total bilirubin, total protein, AST, ALT, alkaline phosphatase, calcium), magnesium, and phosphorus
 - Amylase, lipase, CK, and LDH
 - PT (or INR) and aPTT
- Concomitant medications
- Administration of tebentafusp
- Recording of adverse events
- Research blood

Cycle 3, etc.:

- Physical exam (short)

- Vital signs (pulse, blood pressure, temperature, respiratory rate)
- Relevant laboratory evaluations
 - Complete blood count with differential
 - Comprehensive metabolic panel (sodium, potassium, chloride, bicarbonate, BUN, creatinine, glucose, total protein, albumin, total bilirubin, total protein, AST, ALT, alkaline phosphatase, calcium), magnesium, and phosphorus
 - Amylase, lipase, CK, and LDH
- PT (or INR) and aPTT
- Concomitant medications
- Thyroid function tests (D1 of odd cycles)
- Recording of adverse events
- Administration of tebentafusp
- Recording of adverse events

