- Serum β -HCG or urine pregnancy test for women of child-bearing potential. If the urine test is positive or cannot be confirmed as negative, a serum pregnancy test is required
- Radiographic assessment
 - Occurring every 6 weeks through 48 weeks, and then every 9 weeks thereafter
- Research blood (C3D1, C5D1, C9D1 only)
- Research biopsy (Cycle 3 only)

NOTE: All visits can be obtained ± 2 day of stated time point. Laboratory assessments may occur up to 2 days before infusion. Consecutive infusions of tebentafusp must be administered at least 5 days apart.

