
C2D1 through C2D15 Monitoring requirements for exceptions noted
	
Patients experiencing grade 3 or 4 hypotension at C1D1, C1D8, or C1D15 require hourly vital signs monitoring for minimum of 8 hours after dosing for any doses administered as an outpatient through C3D1. If patients experienced grade \geq 2 hypotension at C1D15, they must be monitored as an inpatient for C2D1, as noted above.

C2 and later cycles- Days 1, 8, and 15 Outpatient monitoring
	
For patients without grade 2 or greater hypotension at C1D15 or grade 3 or 4 hypotension at C1D1, C1D8, or C1D15, outpatient vital signs must be monitored in

	clinic for minimum of 1 hour after infusion with at least 2 post-dose vital signs measurements performed. For patients who have received outpatient treatment with tebentafusp for at least 3 months without an interruption greater than 2 weeks, outpatient monitoring in clinic may be decreased to minimum of 30 minutes after dosing.
Treatment breaks/delays	Patients with break or delay in treatment for > 2 weeks AND with history of a grade 3 or 4 event of hypotension with tebentafusp dosing during the first weeks of treatment will be monitored as an inpatient for the dose subsequent to the break in dosing, with vital signs performed at a minimum of every 4 hours and monitoring for at least 16 hours after dosing.

STUDY CALENDAR

Procedure	Pre-screen	Screening	Cycle 1			Cycle 2	Cycle 3+	EOT	Follow-up
Day of cycle		-28to -1	1	8	15	1	1		
Informed consent	X ¹	X							
HLA typing ¹	X								
Medical history		X							
Concomitant medications		X	Continually assessed						
Physical exam ²		X	X			X	X	X	
Vital signs ³		X	X	X	X	X	X	X	
Height		X							
Weight		X				X	X	X	
Performance status		X							
Hematology panel		X	X			X	X	X	
Chemistry panel		X	X			X	X	X	
Coagulation studies		X						X	
Urinalysis		X						X	
Thyroid function ⁴		X					X (q2cycles)	X	
Pregnancy test ⁵		X					X	X	
Radiographic evaluation ⁶		X					X (q9weeks)		
EKG		X							
Adverse events			Continually assessed						
Biopsy ⁷		X					X	X (optional)	
Research blood ⁸		X				X	X	X	
Tebentafusp ⁹			X	X	X	X	X		
OS assessment ¹⁰									X

1 HLA status will be determined during the pre-screening period. Patients should not sign the Main Study Consent Form and enter Screening until the results of the central assay in Pre-Screening is known.

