Grade 3 or 4	
Hold all doses of tebentafusp until returned to CTCAE Grade ≤ 1.
 
 Institute regular monitoring of liver enzymes until improving or resolved. Administer intravenous steroids (eg, methylprednisolone 0.5 to 1 mg/kg/day or the equivalent) if no improvement within 24 hours. Consider abdominal imaging and a hepatology consult for persistent elevated liver enzymes, onset of clinical signs or symptoms of liver dysfunction (eg, abdominal pain, nausea, vomiting, jaundice), or impact on liver synthetic function. For any Grade 3 elevated liver enzyme elevation, restart tebentafusp only after discussion and written approval from the Medical Monitor. 
Once elevated liver enzymes improve to NCI CTCAE Grade ≤ 1, if restarting tebentafusp, resume treatment as follows:
 
 If elevated liver enzymes occurred in the setting of Grade 3 CRS, resume at the current dose level. Resume escalation once the current dose level is tolerated. If elevated liver enzymes occurred outside the setting of Grade 3 CRS, then resume intrapatient escalation if the current dose level is less than 68 mcg; otherwise, resume treatment at the current dose level if intrapatient escalation has been completed.
Vomiting (graded per CTCAE v5.0)	
Grade 2	
 Administer antiemetic therapy as per institutional standard. Provide IV fluid support and other supportive measures for additional AEs as needed.
Grade 3 or 4	
 Consider holding all doses of tebentafusp until improvement to NCI CTCAE Grade ≤ 1. Administer antiemetic therapy as per institutional standard. Provide IV fluid support and other supportive measures for additional AEs. Consider instituting antiemetic premedication for at least the next dose (eg, ondansetron 8 mg PO/IV or equivalent).
Other Clinically Significant Adverse Events (graded per CTCAE v5.0)	
Treat according to institutional practice and for potential immune-related AEs of Grade ≥ 3 ; treatment with corticosteroids should be considered. Consult the Medical Monitor for further guidance as needed.	
Grade 3 or 4	
Study medication(s) should be permanently discontinued unless AEs improves to Grade 1 or 0, the Investigator believes the overall benefit-risk favors continued treatment, and there is agreement with the Medical Monitor that the participant may restart treatment at the current or reduced dose.

Confidential

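### No liver panel is scheduled at C1D8 (30 mcg) or C1D15 (first 68 mcg), so no scheduled post-dose test can trigger the Appendix B Grade 3-4 liver hold before either escalation step

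*Protocol*

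**What the plan says.** **Schedule.** Section 10.2 lists four items for Day 8 and Day 15 of any cycle: vital signs, concomitant medications, tebentafusp and adverse events. The metabolic panel with AST, ALT, bilirubin and alkaline phosphatase is listed at screening, C1D1, Cycle 2, Cycle 3 onward and end of treatment. The Study Calendar agrees: its "Chemistry panel" row is marked at those visits and is blank at C1D8 and C1D15. The C1D1 panel is a pre-treatment value, because tests done "within 72 hours prior to the first dose of study treatment do not need to be repeated on C1D1". A note in Section 10.2 adds that "Laboratory assessments may occur up to 2 days before infusion"; this sets a time window and adds no test.

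**Dose rules.** Section 6 states that "All dose modifications should be based on the worst preceding toxicity", lets escalation steps be delayed and does not permit reductions from 68 mcg. For Grade 3 or 4 liver enzymes, Appendix B says "Hold all doses of tebentafusp until returned to CTCAE Grade" 1 or less. For elevations outside Grade 3 cytokine release syndrome (CRS), it says "then resume intrapatient escalation if the current dose level is less than 68 mcg".

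**Expected pattern.** Section 7.3.3 says that "A majority (70%) of ALT/AST elevations in the tebentafusp arm occurred within the first 3 infusions". It also says that "Most tebentafusp treated patients who experienced Grade 3 or 4 ALT/AST elevations had improvement to Grade" 1 or less within 7 days.

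**The concern.** A hold that depends on a laboratory grade can act only when a laboratory result exists. Appendix B's resumption clause for patients below 68 mcg has meaning only during escalation, so the hold is meant to work there. Under the schedule as written, nothing measured after the first dose is due before the 30 mcg or the 68 mcg infusion.

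At stake is the safety of a small group: patients with a Grade 3-4 elevation after infusion 1 or 2 that causes no symptoms, prompts no unscheduled test and is still above Grade 1 on the next dosing day. Such a patient could be escalated when the protocol's own rule says to hold. The primary endpoint and its error rates are not involved.

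**Working it through.** **1. Scheduled liver results around escalation**

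| Visit | Dose | Liver panel scheduled? | Age of last required result at dosing |
|---|---|---|---|
| C1D1 (day 1) | 20 mcg | Yes, pre-dose | 0 days, or up to 3 under the 72-hour waiver |
| C1D8 (day 8) | 30 mcg | No | 7 days, or up to 10 |
| C1D15 (day 15) | 68 mcg | No | 14 days, or up to 14 + 3 = 17 |
| C2D1 (day 22) | 68 mcg | Yes | - |

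Visit windows are ignored. The number of scheduled post-dose liver panels before either escalation step is 0. The vital signs and tebentafusp rows of the same calendar do carry marks at C1D8 and C1D15, so the blank chemistry cells are not a reading error. C2D1 falls 7 days after infusion 3 and can trigger the hold, but only from the fourth infusion on.

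**2. Other provisions that might supply a test**

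- Inpatient rule (Sections 5 and 5.1.3, Table 2, calendar footnote 3): it requires vital signs and observation after the dose, and no blood test.
- Appendix B, liver enzymes: regular monitoring starts once an elevation is already known.
- Calendar footnotes: none adds chemistry at these visits.

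Inpatient dosing would probably continue beyond the first six patients. Section 7.3.1 gives Grade 2 or higher CRS as 76% + 0.8% = 76.8%, so the chance that none of six has it is 0.232^6 = 0.00016. This lengthens observation but still adds no liver test.

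**3. Illustrative size**

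Inputs from Section 7.3.3:

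- Grades 1 to 4 across monotherapy studies: 15.0 + 8.3 + 9.7 + 1.8 = 34.8%, which matches the stated figure of about 35%.
- Grade 3-4: 9.7 + 1.8 = 11.5%.
- Share of ALT/AST elevations within the first three infusions: 70%.
- Arm size (Synopsis): 23.

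Assumptions, which the protocol does not supply:

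- The rates carry over from melanoma studies, and the 70% applies to Grade 3-4 events.
- A share *s* of early events follows infusions 1 or 2, with *s* from 1/3 to 1. The low end is included because the hepatic intolerance in Section 5.1.2 (2 of 4 patients) arose at 73 mcg, so events may cluster after infusion 3.
- A fraction *f* is still above Grade 1 at the next dose. *f* = 1 is an upper bound; 1/2 and 1/4 are illustrations.

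Formulas: p = 0.115 × 0.70 × s × f = 0.0805 × s × f. Expected patients = 23p. Chance of at least one = 1 − (1 − p)^23.

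| f | Expected, s = 1/3 | Expected, s = 1 | Chance of at least one |
|---|---|---|---|
| 1 (upper bound) | 0.62 | 1.85 | - |
| 1/2 | 0.31 | 0.93 | 27% to 61% |
| 1/4 | 0.15 | 0.46 | 14% to 37% |

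Example: s = 1 and f = 1/2 give p = 0.0403, so 23p = 0.93 and 1 − 0.9597^23 = 0.61.

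The 11.5% covers all liver-test and hepatotoxicity events, not only transaminases. Scaling by the AST share (17.6/34.8) replaces 0.0805 with 0.115 × 17.6/34.8 × 0.70 = 0.0407:

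| f | Expected, s = 1/3 to 1 | Chance of at least one |
|---|---|---|
| 1 (upper bound) | 0.31 to 0.94 | - |
| 1/2 | 0.16 to 0.47 | 15% to 38% |
| 1/4 | 0.08 to 0.23 | 8% to 21% |

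Symptomatic cases found by unscheduled tests would lower all of these figures.

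**The case against.** The case for leaving the schedule alone has five parts.

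- **Benign course.** Section 7.3.3 judges liver-test increases not clinically relevant in either arm of the randomized study. It reports no deaths from ALT/AST elevations, more than 90% of patients continuing past their worst grade, and milder recurrences on re-dosing. Section 5.1.2 reports no significant elevations in six patients at 68 mcg and reversible events at 73 mcg. This stands and limits the severity. It does not show that escalating without a liver result is safe.
- **Blood is likely to be drawn anyway.** About 89% of patients in that study had CRS, mostly with the first three infusions, and Appendix B's CRS guidance on infection, neutropenia and electrolytes presupposes blood work. This will catch some cases. It does not require AST or ALT, and a draw close to the infusion can miss a later rise.
- **The Section 10.2 list is incomplete.** Calendar footnote 2 places a short physical examination at C1D8 and C1D15 that the list omits. True, but the calendar itself also leaves chemistry blank there.
- **The numbers are mostly assumed.** The pooled Grade 3-4 rate may include regimens without step-up dosing, the 70% is all-grade from one study, and the persistence fractions have no source. This stands, so the figures show scale and are not estimates.
- **A positive test has consequences.** Appendix B then brings a hold, intravenous steroids if there is no improvement within 24 hours and, after Grade 3, written approval to restart. Section 5.2 says steroids interfere with the drug's action. These are real costs, but they follow from the rule the protocol already chose.

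**Conclusion.** The concern holds. Section 10.2 and the calendar agree with each other, and together they leave the Grade 3-4 liver hold without a scheduled trigger at both escalation steps. That conclusion rests on the text alone.

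The size is small and uncertain. Probably fewer than one of 23 patients would be escalated against the hold rule: 0.2 to 0.9 if one-quarter to one-half of Grade 3-4 elevations persist to the next dose, or 0.1 to 0.5 if scaled to AST alone. The upper bound of 1.9 counts patients who may have recovered and need no hold. The protocol gives neither the days from infusion to onset nor the split of early events between infusions, so the true share is unknown. Because most Grade 3-4 elevations improve within 7 days, many would neither need the hold nor appear on an added panel. The change is advisable for patient safety, but the validity of the primary analysis does not depend on it.

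**What to change.** In Section 10.2, add a liver panel (AST, ALT, bilirubin, alkaline phosphatase) for C1D8 and C1D15, and mark both visits in the calendar's chemistry row. Draw the sample within the existing window of up to 2 days before infusion, and require that the result be reviewed before the dose is given. The Appendix B hold and resumption rules stay as they are.

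The cost is at most 2 × 23 = 46 blood tests at visits already held for infusion, and an occasional dose delayed while a result is awaited. In a patient who tests positive, the hold and any steroid treatment already prescribed by Appendix B would follow.

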7.4 Drug Interactions

No drug-drug interactions have been observed with tebentafusp.

7.5 Use During Pregnancy and Lactation

No data are available with tebentafusp use in pregnant or lactating women. No animal reproductive and developmental toxicity studies have been conducted with tebentafusp to assess whether it can cause fetal harm when administered to a pregnant woman. It is not known if tebentafusp has the potential to be transferred to the fetus or human milk. Therefore, tebentafusp is not recommended for women who are pregnant or breast feeding, and contraception requirements are described in the individual clinical study protocols.

7.6 Overdose

No antidote is known for tebentafusp, nor has it been defined what constitutes an overdose. However, inadvertent incorrect dosing, such as administration of a higher dose than stated in the protocol, should be rigorously monitored for potential (serious) adverse reactions. Patients experiencing toxicity upon incorrect dosing or overdosing must be treated at the discretion of the treating physician with adequate supportive care as indicated by the symptoms observed in the patient which generally should include IV corticosteroid therapy. Patients will have to be followed until full recovery or confirmed stabilization of the events.

